### **Treatment of Subjects**

The research takes place over six months in total. It will be necessary for each subject to come to the clinic at HCTM for an initial screening and three-monthly follow-ups. During these visits, they will undergo a routine screening which involves blood collection procedure, a liver fibrosis scan, and a dual-energy absorptiometry scan and they will be informed of the results of the tests conducted. They will also be given either the test supplement or the placebo for the management of AFLD. They will be required to take 2 softgels containing 200 mg TRF or placebo orally, each after breakfast (one softgel) or dinner (one softgel). The assignment of TRF and placebo will be random, and the physician and enumerator attending you will not be aware of your assigned treatment. At the end of six months, all data will be collected and analysed, and the research will be completed.

Identifying specific barriers for each subject and adopting suitable techniques to overcome them will be necessary to improve the subject's compliance and medication adherence. Health care professionals involved in this study such as physicians and nurses have significant role in their daily practice to improve subject medication adherence. We will give medication reminders via text or email to our study subjects. The subjects may keep a diary, or they can bring all unused or part-used medication/vials and packaging from used medication at each follow-up visits for soft gel capsule counting and to discuss their compliance. Another method is to keep track of their medications with a "pill card" or "medication calendar." The subjects will be required to bring their "pill cards" to every appointment, and/or we may ask them to keep a monthly calendar on which they will mark each day when they took their capsules.

Subjects' non-adherence to alcohol abstinence during the duration of this study might also pose a risk to this study. We will try to minimise this risk by closely monitoring all study subjects to detect any withdrawal symptoms and offering them comprehensive care and the necessary psychological counseling or pharmacotherapy.

### **Adverse Events (AEs), Serious Adverse Events (SAEs), and Suspected Unexpected Serious Adverse Reactions (SUSARs)**

While the possibility of having some unwanted side effects and unexpected events related to the tocotrienol supplementation and the treatment procedures is very low, the enrolled subjects should still be aware of the possibility. We will try to decrease the chances of this event occurring through close monitoring of all subjects but if something unexpected happens, we will provide them with proper care and appropriate treatment. We may use some other medicines to decrease the symptoms of the side effects or reactions. Or we may stop the use of this supplement and end their participation. If this is necessary, we will discuss it with the

subjects, and they will always be consulted before we move on to the next step. Given that the subjects must adhere to alcohol abstinence throughout the course of this study, if they experience any withdrawal symptoms, we will give them supportive care and medications as part of the treatment regimens used in alcohol withdrawal states to minimise the symptoms and prevent complications.

Our qualified physician, who is a co-investigator for the trial, will be responsible for all trial-related medical decisions. During and following a subject's participation in this trial, we will ensure that adequate medical care is provided to a subject for any adverse events, including clinically significant laboratory values, related to the trial. We will inform a subject when medical care is needed for intercurrent illness (es) of which we become aware. We will also recommend the subjects to inform their primary physician about their participation in this trial if the subject has a primary physician and if the subject agrees to the primary physician being informed, while fully respecting the subject's rights.

#### Reporting Procedures for Adverse Events

Adverse events and/or laboratory abnormalities identified as critical to safety evaluations will be reported to the sponsor according to the reporting requirements and within the specified time periods.

All AEs occurring during the trial that are observed by the Investigator or reported by the trial subject will be reported on the trial case report form (CRF), whether or not attributed to trial medication. The following information will be reported on the CRF: description, date of onset and end date, severity, assessment of relatedness to trial medication, other suspect drug or device and action taken. Follow-up information should be provided as necessary.

The severity of events will be assessed on the following scale: 1 = mild, 2 = moderate, 3 = severe.

Non-serious AEs considered related to the trial medication as judged by a medically qualified investigator or the Sponsor will be followed up either until resolution, or the event is considered stable.

It will be left to the clinical judgment of our medical officer to decide whether or not an AE is of sufficient severity to require the participant's removal from treatment. A participant may also voluntarily withdraw from treatment due to what he or she perceives as an intolerable AE. If either of these occurs, the participant will be given appropriate care under medical supervision until symptoms cease, or the condition becomes stable.

#### Reporting Procedures for Serious Adverse Events

All SAEs must be reported on the SAE Reporting Form to the Sponsor or delegate immediately or within 24 hours of Site Study Team becoming aware of the event being defined as serious. The immediate reports will be followed promptly by detailed, written reports. The immediate and follow-up reports should identify subjects by unique code numbers assigned to the trial subjects rather than by the subjects' names, personal identification numbers, and/or addresses, in accordance with the applicable regulatory requirement(s) related to the reporting of unexpected serious adverse drug reactions to the regulatory authority(ies) and the IRB/IEC.

Review of SAEs must be timely, taking into account the reporting timeline for a potential SUSAR. SAEs that are reported late must be accompanied by an explanation for this.

### SUSAR Reporting

All SUSARs will be reported by the sponsor delegate to the relevant Regulatory Authority and to the REC and other parties as applicable. For fatal and life-threatening SUSARS, this will be done no later than 7 calendar days after the Sponsor or delegate is first aware of the reaction. Any additional relevant information will be reported within 8 calendar days of the initial report. All other SUSARs will be reported within 15 calendar days.

Treatment codes will be un-blinded for specific participants. Additionally, principal investigator will be informed of all SUSARs for the relevant IMP for all studies with the same sponsor, whether or not the event occurred in the current trial.

### **STATISTICAL ANALYSIS**

Normality of the data will be assessed through Shapiro-Wilk test. Since the study adopts a time x group design, mixed-design ANOVA will be used to compare the effects across time (within group) and between treatment groups. Small effect analysis will be used as the pairwise post hoc analysis. If the data is skewed, the data will be analysed with Kruskal Wallis test and Mann Whitney U-test with Bonferroni correction for type-1 error. All analyses will be performed using Statistical Package for Social Sciences version 23 (IBM, Armonk, USA). The data will be presented as mean (standard deviation). A p-value less than 0.05 is considered statistical significance.

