### Primary Outcome Measures:

1. Change from baseline in Liver Enzyme Profile (Aspartate Aminotransferase [AST], Alanine Aminotransferase [ALT], and Gamma-Glutamyl Transferase [GGT]) at 3 and 6 months. Measured in units per liter (U/L) and reported as absolute and percentage change. Lower values indicate improved liver function.
2. Between-group difference in Liver Enzyme Profile (AST, ALT, GGT) at 3 and 6 months (Tocotrienol-Rich Fraction vs placebo). Measured in U/L. Lower values indicate improvement.
3. Change from baseline in Fatty Liver Index (FLI) at 3 and 6 months. Unitless score (range 0–100). Higher scores indicate greater hepatic steatosis (worse outcome). Reported as absolute and percentage change.
4. Between-group difference in Fatty Liver Index (FLI) at 3 and 6 months (Tocotrienol-Rich Fraction vs placebo). Range 0–100. Higher scores indicate worse steatosis.
5. Change from baseline in Liver Stiffness Measurement using Transient Elastography (FibroScan® score) at 3 and 6 months. Measured in kilopascals (kPa; typical range 2–75). Higher values indicate greater fibrosis. Reported as absolute and percentage change.
6. Between-group difference in Liver Stiffness Measurement (FibroScan® score) at 3 and 6 months (Tocotrienol-Rich Fraction vs placebo). Measured in kPa. Higher values indicate worse fibrosis.

\*Aspartate aminotransferase (AST) is usually used to detect liver damage. It is often ordered in conjunction with other liver enzymes, alanine aminotransferase (ALT) and gamma-glutamyl transpeptidase (GGT), or as part of a liver panel or comprehensive metabolic panel (CMP) to screen for and/or help diagnose liver disorders. The changes in these liver enzymes can also be used to monitor the compliance of patients toward alcohol abstinence.

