## SAMPLE SIZE CALCULATION

Sample size calculation was based on the comparison of two means derived from the effects of tocotrienol on fatty liver index (FLI) in patients with non-alcoholic fatty liver disease (NAFLD) (21). This is because the effectiveness of tocotrienol in alcoholic hepatitis has not been evaluated previously.

Formula of calculating sample size in clinical trial (22):

$$n = [(Z\alpha/2 + Z\beta)^2 \times \{2(\sigma)^2\}] / (\mu_1 - \mu_2)^2$$

Where:

$n$  = sample size required in each group

$\mu_1$  = mean of FLI for tocotrienol group = 12.82  $\mu_2$  = mean of FLI for placebo group = 3.86

$\sigma$  = standard deviation = 7.0

$Z\alpha$ : This depends on level of significance, for 5% this is 1.96  $Z\beta$ : This depends on power, for 80% this is 0.84

$$n = [(1.96 + 0.84)^2 \times \{2(7.0)^2\}] / (12.82 - 3.86)^2$$

The sample size calculated is 10 per group. Taking into account 20% of subjects might be lost to follow up, the number of each group is adjusted to 13. Hence, the total sample size required for this study is 26 individuals.

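### The only parametric analysis named, a mixed-design ANOVA, in its usual form drops every patient with a missed visit, although months 3 and 6 are both primary and 20% loss is expected

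*Protocol*

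**What the plan says.** The Statistical Analysis section fixes the parametric method: "mixed-design ANOVA will be used to compare the effects across time (within group) and between treatment groups". It justifies the choice by the time-by-group design and names SPSS version 23, but no SPSS procedure. The only alternative depends on the distribution of the data: "If the data is skewed, the data will be analysed with Kruskal Wallis test and Mann Whitney U-test with Bonferroni correction for type-1 error". Nothing is said about patients with incomplete visits.

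Primary Outcome Measures sets both post-baseline visits as primary for AST, ALT, GGT, FLI and liver stiffness. One entry, for example, is "Between-group difference in Fatty Liver Index (FLI) at 3 and 6 months". Sample Size Calculation expects incomplete follow-up: "Taking into account 20% of subjects might be lost to follow up, the number of each group is adjusted to 13".

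Three further statements bear on this:
- The stopping rules end participation for subjects who do not stay abstinent.
- The note under Primary Outcome Measures says that changes in the enzymes can serve to monitor abstinence.
- Withdrawal criteria says that withdrawn subjects are not replaced and, in the paragraph on subjects who choose to stop, that their existing data and samples are left out of the final analysis and discarded.

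**The concern.** A mixed-design ANOVA as usually run (repeated-measures general linear model) takes one row per patient and needs every cell of that row filled. A patient with baseline and month-3 values but no month-6 value contributes nothing, not even to the month-3 comparison. The protocol makes month 3 primary in its own right and plans for one patient in five to be lost, so the method it fixes sits badly with its own design.

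Two things are at stake. The first is precision: primary measurements already collected and paid for are not used. The second is bias. A complete-case comparison is generally safe only if loss is unrelated to outcome. Here relapse to drinking can end participation and, by the protocol's own note, relapse shows in the primary enzymes. Loss may therefore be related to outcome.

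For subjects who choose to stop, the discard sentence already removes the data. For a single missed visit, an unusable sample or scan, or a patient who simply stops attending, that sentence does not clearly apply, and the ANOVA alone causes the exclusion.

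**Working it through.** **Inputs.** From Sample Size Calculation: FLI means 12.82 and 3.86 (difference 8.96), SD 7.0, z-values 1.96 and 0.84, 20% loss, 13 per group. From Primary Outcome Measures: months 3 and 6. Not given in the documents, so assumed: the correlation between visits (range 0.3 to 0.8) and the split of the loss before and after month 3.

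**1. The plan's own figure.** n = (1.96 + 0.84)² × 2 × 7.0² / 8.96² = 9.57, rounded up to 10 per group. 10 / 0.8 = 12.5, rounded up to 13 per group, 26 in total. The stated size is reproduced.

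**2. Patients in a complete-case ANOVA.** 26 × 0.8 = 20.8, so about 21 of 26; 26 × 0.2 = 5.2, so about 5 are excluded. In whole patients per group, 13 falls to about 10.

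**3. Month-3 precision if all loss follows month 3.** All 26 month-3 values exist, but only those of completers are used.
- With 20.8 completers: SE ratio = √(26 / 20.8) = 1.12.
- With 10 of 13 per group: SE ratio = √(13 / 10) = 1.14, a variance ratio of 10 / 13 = 0.77 in favour of using all values.

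This is the upper end for 20% loss. If all loss precedes month 3, there are no month-3 values to recover and the ratio is 1.

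**4. Month-6 precision in the same case.** With 10 complete patients per group, 3 seen only at month 3, and correlation ρ between the two post-baseline measurements (covariance taken as known), the variance of the month-6 mean relative to complete cases is 1 − ρ² × 3/13.

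| ρ (assumed) | Variance ratio | SE reduction |
|---|---|---|
| 0.3 | 0.98 | 1% |
| 0.5 | 0.94 | 3% |
| 0.7 | 0.89 | 6% |
| 0.8 | 0.85 | 8% |

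**5. Possible bias.** The documents do not allow this to be sized. As an illustration only, a simulation assumed 13 per group, SD 7, a true month-3 effect of 4.48 (half of 8.96), loss split around month 3, later loss more likely with a worse month-3 value, and visit correlations of 0.4 to 0.8. It gave a complete-case month-3 difference in change of 4.15 to 4.37. The shortfall is 0.11 to 0.33 FLI points, or 2% to 7%. With 10.4 completers per group, the standard error of that difference is 7 × √(2(1 − ρ)) × √(2/10.4), which is 3.4 at ρ = 0.4 and 1.9 at ρ = 0.8. The illustrated bias is thus under a fifth of a standard error, and it depends on how strongly loss is assumed to follow outcome.

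**6. Power.** On the protocol's normal formula, 10 completers per group give 81.7%, above the 80% target; all 13 give 90.4%. A noncentral t calculation gives 77.2% and 87.9%. The gap between the two methods comes from the normal approximation, not from the handling of missing visits.

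**The case against.** The strongest reply is that the protocol states no complete-case rule. List-wise deletion belongs to the usual procedure, and a statistical analysis plan that is not at hand could add imputation or fit the time-by-group design as a mixed model. It is right that nothing in the protocol orders deletion. But the protocol does choose a method and gives a reason for it, and either repair would amount to the change asked for here.

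Other parts of the reply stand in full, and they limit the point:
- A reader might infer that the whole expected 20% lose month-3 data. The 20% is not split by time, and a patient lost before month 3 has none to lose.
- A reader might infer that such data can never be used. The Mann-Whitney fallback, run visit by visit, could use them. The set of patients analysed would then vary between outcomes with the result of a normality test, which is awkward but is not the same as total loss.
- A reader might infer that the trial is underpowered because of the ANOVA. It is not: the increase from 10 to 13 per group was made for this loss.
- A reader might take missing completely at random as the only condition under which complete cases are valid. Loss that depends only on treatment arm would also leave the group comparison unbiased. The documents suggest a route from outcome to loss through abstinence; they do not show that poor responders leave.
- Changing the model alone recovers nothing for subjects who choose to stop, because their data are discarded under Withdrawal criteria.

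**Conclusion.** The point holds in limited form. The one parametric method that the protocol fixes is, as usually run, a complete-case analysis of about 21 of 26 patients. It leaves unused valid primary values from patients with a missed visit or lost after month 3. The cost in the month-3 standard error is at most about 12% to 14%, reached only if all loss follows month 3, and zero if all of it comes earlier. At month 6 the recoverable part is about 1% to 8% of the standard error for assumed correlations of 0.3 to 0.8. Bias is plausible, given the link between abstinence, termination and the enzymes, but it cannot be sized from the documents and was small in the illustration. The sample size and stated power are not in error. This merits a change because a better analysis is available at little cost, not because the present one invalidates the trial.

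**What to change.** In Statistical Analysis, replace the mixed-design ANOVA with a linear mixed model for repeated measures (SPSS MIXED, REML, unstructured covariance). Use month-3 and month-6 values as responses, baseline as covariate, and treatment, visit and treatment-by-visit as fixed effects. Include every randomised patient with at least one post-baseline value, and read the month-3 and month-6 treatment differences from this one model.

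Align the data-discard sentence in Withdrawal criteria with this rule. As it stands, the two would contradict each other for subjects who choose to stop.

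Cost: one paragraph in the analysis section and one sentence in Withdrawal criteria, with any matching statement made to participants if there is one (consent pages were not available). No extra patients, visits, tests or software are needed. The model relies on data being missing at random, which cannot be verified but is weaker than what the complete-case analysis generally needs. The choice should be fixed before unblinding: with 26 patients, a later decision on how to treat incomplete ones could affect the result.

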### Research Gap

Concerns about the high prevalence of AFLD globally and the not fully understood reasons for its progression to more severe forms of liver diseases have led to the initiation of this interventional, double-blind placebo-controlled study. The aim of the investigation was to

evaluate the activity of tocotrienols in normalising hepatic echogenic response in adults with AFLD.

Currently, there are no effective treatment for alcoholic fatty liver disease apart from alcohol abstinence and making some lifestyle changes to control or reverse the fat build-up in the liver. An antioxidant and anti-inflammatory agent are speculated to enhance the healing of liver after alcohol abstinence, but this concept has not been effectively demonstrated in a clinical trial. Therefore, new therapies are urgently needed to prevent the progression of AFLD. Tocotrienol are well established for its potent antioxidant capabilities, while evidence had also shown its positive effects on inflammation. Thus, this study will validate the efficacy of tocotrienol in AFLD and its related morbidity, thereby producing data for subsequent phases of clinical trials. The findings of this study will also enhance the medicinal values of palm tocotrienol and diversify the usage of palm-based products in sustaining the Malaysian palm industry.

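### The protocol orders mean (SD) for all data, including data it sends to rank tests, and names no estimate that matches those tests

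*Protocol*

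**What the plan says.** The Statistical Analysis section checks normality with Shapiro-Wilk and uses a mixed-design ANOVA by default. For data that fail the check it states: "If the data is skewed, the data will be analysed with Kruskal Wallis test and Mann Whitney U-test with Bonferroni correction for type-1 error". Two sentences later comes the reporting rule, with no exception for such data: "The data will be presented as mean (standard deviation"). The criterion for inference follows: "A p-value less than 0.05 is considered statistical significance".

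The rule reaches the primary outcomes. Under Primary Outcome Measures the protocol lists "Between-group difference in Liver Enzyme Profile (AST, ALT, GGT) at 3 and 6 months (Tocotrienol-Rich Fraction vs placebo). Measured in U/L", "Between-group difference in Fatty Liver Index (FLI) at 3 and 6 months (Tocotrienol-Rich Fraction vs placebo") and "Between-group difference in Liver Stiffness Measurement (FibroScan® score) at 3 and 6 months (Tocotrienol-Rich Fraction vs placebo). Measured in kPa". The same list asks for changes from baseline in absolute and percentage terms. The plasma cytokines under Secondary Outcome Measures fall under the same reporting rule.

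The protocol mentions no median, interquartile range or rank-based estimate of difference anywhere.

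**The concern.** Within one paragraph the plan decides that certain data are too skewed for a comparison of means, and then requires those data to be shown as means. This is a stated rule rather than a detail left open: an analysis plan that used medians for these measures would depart from the protocol.

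A Mann-Whitney test compares how often a patient on one arm has a higher value than a patient on the other. An arm mean in a small skewed sample depends heavily on its largest values. A reader who subtracts the two reported means gets a difference that the test did not assess, with a size and sometimes a sign of its own. The Research Gap section gives the purpose of the trial as "thereby producing data for subsequent phases of clinical trials", and for that purpose the reported effect should be the one that was tested.

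**Working it through.** **1. Arm size.** From the Sample Size Calculation section: FLI values 12.82 and 3.86, SD 7.0, multipliers 1.96 and 0.84.

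n = (1.96 + 0.84)² × 2 × 7.0² / (12.82 − 3.86)² = 7.84 × 98 / 80.28 = 9.57, so 10 per arm. With 20% loss, 10 / 0.8 = 12.5, so 13 per arm and 26 in total. The plan's figures reproduce. About 10 evaluable patients per arm is the size used below, unless stated otherwise.

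**2. A constructed example.** These are invented GGT-like values in U/L, 10 per arm, chosen only to show the mechanism.

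- TRF: 48, 52, 55, 58, 61, 64, 70, 76, 83, 640
- Placebo: 88, 92, 95, 99, 104, 108, 113, 119, 126, 134

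| Summary | TRF | Placebo | TRF − placebo |
|---|---|---|---|
| Mean (SD) | 120.7 (182.8) | 107.8 (15.2) | +12.9 |
| Median | 62.5 | 106.0 | −43.5 |
| Hodges-Lehmann | | | −42 (exact 95.7% CI −56 to −25) |

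Shapiro-Wilk gives p < 0.001 in the TRF arm, so the rank route applies. In 90 of the 100 TRF-placebo pairs the TRF value is lower (U = 10), and the exact Mann-Whitney p is 0.0015 in favour of TRF. The report that the protocol prescribes would show a higher mean on TRF beside that p-value. The Hodges-Lehmann estimate is the median of the 100 pairwise differences, so its sign follows the Mann-Whitney statistic.

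**3. How well mean (SD) describes such data.** The protocol gives no distribution for enzymes or cytokines, so this is an assumption: log-normal levels at a visit, equal log-SD of 0.8 or 1.0, TRF/placebo ratio 0.7, 10 per arm.

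Mean − 2 SD is negative when SD/mean exceeds 0.5. For log-normal data SD/mean = √(exp(σ²) − 1), which is √(1.896 − 1) = 0.95 at σ = 0.8 and √(2.718 − 1) = 1.31 at σ = 1.0. In simulation (40,000 trials per setting) the sample mean minus 2 SD is below zero in 91% and 98% of TRF arms, although the measures cannot be negative. This check concerns levels; a change from baseline can be negative.

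**4. How often mean and rank directions differ.** Same assumptions:

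| | log-SD 0.8 | log-SD 1.0 |
|---|---|---|
| Directions differ, all trials | about 11% | about 14.5% |
| TRF mean higher, significant rank test favours TRF | 0.015% | 0.055% |

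The second row counts 3 and 11 of 20,000 trials, so it should be read as well under 0.1%. Rank-test power in these settings is 10% to 14%, and 0.1% to 0.5% of significant trials are discordant. Significant discordant trials are therefore at most 0.14 × 0.005 = 0.07% of all trials, and nearly all of the 11% to 14.5% are non-significant.

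**5. Sensitivity to spread** (10 or 13 per arm, 20,000 trials per setting, unadjusted two-sided 5% test).

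- Equal log-SD 0.5 to 1.5, log shift 0 to 1.0: directions differ in 0% to 27% of all trials and in 0% to 2.6% of significant ones.
- Unequal spread (log-SD 0.6 on placebo, 1.2 to 1.5 on TRF, log shift 0.5 to 0.8): 20% to 51% of all trials and 3.5% to 20% of significant ones.

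**The case against.** Three stronger readings are tempting, and the protocol does not support them.

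- *No treatment difference will be produced.* Primary Outcome Measures names between-group differences in U/L, FLI points and kPa, and adds absolute and percentage change. What is missing is an estimate that matches the rank test.
- *The absence of a confidence interval is itself a defect.* The protocol names none but excludes none, and a separate analysis plan may supply it. An interval belongs in the remedy only.
- *Published means will often contradict a significant test.* With equal spread this is very rare. The higher rates need a heavier tail in one arm, which the protocol neither states nor implies. The example in the working shows that contradiction is possible, not that it is likely.

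It can also be said that most disagreements in sign occur in null results, where direction is largely noise, and that every distribution used here is assumed. Both statements are right, and they limit the size of the point. It can further be said that the matter is one of presentation: no test, error rate or sample size depends on it, and it can be corrected before reporting. That also stands, and is why the point is minor.

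None of this removes the mismatch within the section. In a non-significant small trial the arm summaries are much of what a reader has to go on, and for skewed measures the protocol prescribes summaries that do not describe the data well.

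**Conclusion.** The point holds in a limited form. The protocol requires mean (SD) for all data, including data it has judged too skewed for ANOVA, and names no summary or difference that fits the rank tests for its primary between-group comparisons.

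The firmer consequence is poor description: under the assumed log-normal levels, mean (SD) implies impossible negative values in 91% to 98% of TRF arms. A conflict of direction between means and ranks is less frequent, at about 11% to 14.5% of trials, and almost always accompanies a non-significant result. A conflict with a significant rank test is a real concern only if the arms differ markedly in spread.

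The contradiction in the text needs no assumption. The percentages rest on log-normal levels, a ratio of 0.7, equal spread and 10 patients per arm, none of which except the arm size comes from the protocol. Severity is minor.

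**What to change.** Replace the reporting sentence in the Statistical Analysis section with:

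> Approximately normal data: mean (SD) per arm, with the TRF-placebo mean difference and 95% CI from the analysis model. Data analysed by rank tests: median (IQR) per arm, with the Hodges-Lehmann TRF-placebo difference and 95% CI at months 3 and 6.

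The cost is slightly more analysis and reporting work. The sample size stays at 10 evaluable and 13 randomised per arm, and the tests and trial conduct are unchanged.
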